5. ANALYSIS SETS

For purposes of analysis, the analysis sets in this section are defined for all sub-protocols. Specific additional analysis sets may be defined in sub-protocols or their corresponding sub-protocol SAPs.

5.1. FULL ANALYSIS SET

For each sub-protocol, the full analysis set (FAS) will contain all patients who were randomized to the sub-protocol candidate agent plus SoC arm as well as all patients who were randomized to any placebo plus SoC arm included in the control arm of the candidate agent (refer to Section 4.5).

[figure not shown]
For displays and analyses based on FAS, patients will be classified according to randomized treatment.

5.2. SAFETY ANALYSIS SET

For each sub-protocol, the safety analysis set will contain all patients included in the FAS (refer to Section 5.1) who took at least one dose study drug. If there is any doubt whether a patient was treated or not, he/she will be assumed treated with the study drug for the purposes of analysis.

For analyses and displays based on the safety analysis set, patients will be classified according to the actual treatment received (based on data captured on the interactive web response system [IWRS]). That is, a patient randomized to a placebo plus SoC arm who received at least one dose of the candidate agent during the course of the study will be classified under the candidate agent plus SoC arm and a patient randomized to the candidate agent plus SoC arm who never received the candidate agent will be classified under the control arm.

If a patient randomized to the placebo arm of sub-protocol X is selected for the control arm of sub-protocol Y (refer to Section 4.5) and begins taking the candidate agent of sub-protocol Y for another approved indication after randomization as a concomitant medication (based on data captured on the *Concomitant Medications* page of the eCRF), this patient will still be presented under the control arm of sub-protocol Y for summaries based on the safety analysis set and a listing of all AEs will be provided for such patients, if they exist.

5.3. PROCESS FOR ANALYSIS SET ASSIGNMENT

The analysis sets that will be used to summarize, analyze, and list the data collected during the course of this study are all defined based on objective criteria only. That is, none of the analysis set definitions included in this SAP contains subjective criteria (e.g., major protocol deviation potentially having an impact on the efficacy data). Hence, the authorization of this SAP will also stand for the agreement and authorization of the inclusion/exclusion of each patient in each of these analysis sets.

If analysis sets defined in a sub-protocol SAP involve subjective criteria, the process for analysis set assignment prior to interim, primary or final database locks will be detailed in the sub-protocol SAPs.

6. GENERAL CONSIDERATIONS

6.1. STUDY DAY

Study day will be calculated from the day of the first dose of the study drug for patients who received at least one dose of study drug and from the day of randomization for randomized patients who were never dosed, and will be used to show start/stop day of assessments and events.

Study day will be computed as follows:

- Study Day = (Date of interest – Date of first dose of study drug/randomization, as appropriate) + 1 if the date of interest is on or after the date of first dose of study drug/randomization, as appropriate;
- Study Day = (Date of interest – Date of first dose of study drug/randomization, as appropriate) if the date of interest is prior to the date of first dose of study drug/randomization, as appropriate.

Based on these formula, Study Day 1 will be the day of the first dose of the study drug for patients who received at least one dose of study drug and the day of randomization for randomized patients who were never dosed.

In the situation where the date of interest is partial or missing, Study Day and any corresponding durations will be considered as missing in the analyses and the date of interest will be presented as partial or missing in the listings.

6.2. BASELINE

Unless otherwise specified, baseline is defined as the last non-missing measurement (including unscheduled measurements) taken prior to the first dose of study drug for patients who received at least one dose of study drug and as the last non-missing measurement (including unscheduled measurements) taken prior to randomization for randomized patients who were never dosed. In the case where the last non-missing measurement and first dose of study drug/randomization dates coincide, time will be considered. If time is not collected, missing or unknown, measurements taken on the same day of the first dose, or same day as randomization for subjects not dosed, will be considered as the baseline measurement unless the assessment was scheduled to be collected post-first dose/post-randomization in the master/sub-protocol (refer to Section 3.2).

For adverse events (AEs) commencing on the date of the first dose of study drug/randomization, time of onset of the AE will be considered when determining if the event was pre-baseline (not treatment-emergent) or post-baseline (treatment-emergent). Medications that are ongoing or commencing on the date of the first dose of study drug/randomization will be considered as concomitant medications (refer to Section 13) . Partial or completely missing AE and medication dates will be handled as described in Appendix 1.

6.3. UNSCHEDULED VISITS, RETESTS, DISCHARGE, AND EARLY TERMINATION DATA

For by-visit summaries, data recorded at the nominal visit will be presented. That is, unscheduled visits will not be included in by-visit summaries but might contribute to the baseline timepoint (refer to Section 6.2) and/or worst/maximum/minimum post-baseline value, where required (e.g., shift table).

In case of a retest when retest is defined as having a blood sample tested twice, the latest available measurement for that blood sample will be used for the by-visit summaries. In case of a retest when retest is defined as having two blood samples collected on the same day, results from the last blood sample will be used for the by-visit summaries.

Refer to Section 6.4 for the conventions to map discharge and early termination data to protocol-defined visit windows. Discharge and early termination data might also contribute to the worst/maximum/minimum post-baseline value, where required (e.g. shift table).

Listings will include all scheduled, unscheduled, retest, discharge, and early discontinuation data.

CCI

PPD

Version Number: Amendment 1, v1.0
Version Date: 23Apr2021

CCI

6.4. WINDOWING CONVENTIONS

Discharge and early termination data will be mapped based on the scheduled Study Day of each scheduled visit with adjusted protocol-defined visit window, as specified in the appropriate sub-protocol schedule of activities (refer to Section 3.2).

If discharge or early termination data are mapped to a scheduled visit for which data from the scheduled visit are also available (i.e., non-missing), the data collected at the scheduled visit will be used in the by-visit summaries. If discharge or early termination data are mapped to a scheduled visit for which data from the scheduled visit are not available (i.e., missing), data from the discharge or early termination visit will be used in the by-visit summaries, as applicable.

6.5. COMMON CALCULATIONS

Change from baseline will be calculated as:

- Change from baseline = Observed value at post-baseline visit – Baseline value

Percent change from baseline will be calculated as:

- Percent change from baseline = (Change from baseline / Baseline value) * 100

7. STATISTICAL CONSIDERATIONS

For continuous data, descriptive statistics (i.e., n [number of patients with available data], mean, standard deviation [SD], minimum, 25th percentile (Q1), median, 75th percentile (Q3), and maximum values) will be presented by treatment arm and visit, when applicable.

For categorical data, the number and percentage of patients in each category will be presented by treatment arm and visit, when applicable.

7.1. SAMPLE SIZE CALCULATION

A total of up to 350 patients are planned to be randomized to each candidate agent plus SoC. Simultaneously, patients will be randomized to placebo plus SoC throughout the course of the study. The subset of shared placebo

CCI

PPD

Version Number: Amendment 1, v1.0
Version Date: 23Apr2021

CCI

plus SoC treatment arm, regardless of which sub-protocol the placebo belongs, enrolled concurrently to an active agent with matching inclusion/exclusion criteria will serve as comparator (refer to Section 4.5). The primary efficacy endpoint to compare selected treatment plus SoC to placebo plus SoC included in the control arm will be the time to confirmed clinical recovery through Day 29 i.e., fit for discharged (defined by achieving a score of 6, 7 or 8 on the 8-point ordinal scale for clinical severity status), without re-hospitalization through Day 29 (refer to Section 16.1.1).

Assuming a median time to confirmed clinical recovery of 11 days for patients randomized to a candidate agent plus SoC arm compared with 15 days for those randomized to its concurrent placebo plus SoC arm, 350 patients are needed per arm in order to observe 490 confirmed clinical recovery events between the 2 treatment arms being compared at the primary analysis of a sub-protocol. This sample size will provide approximately 88% power to detect a hazard ratio (HR) of 1.364 for the occurrence of the confirmed clinical recovery events, when comparing each candidate agent plus SoC with their concurrent placebo plus SoC arm, at a one-sided significance level of 0.025.

This sample size will provide the following information about the key secondary efficacy endpoints:

- Assuming the oxygen-free recovery rate at Day 29 is 65% for the concurrent placebo plus SoC arm of a candidate agent, a sample size of 350 patients per arm will provide approximately 80% power to detect a 9.7% absolute increase in the proportion of patients who have oxygen-free recovery at Day 29 in the candidate agent plus SoC arm;
- Assuming 70% of patients randomized to the concurrent placebo plus SoC arm of a candidate agent achieve at least 2-point improvement from baseline on the 8-point ordinal scale or are fit for discharge at Day 29, 350 patients per arm will provide approximately 80% power to detect a 9.2% absolute increase in this proportion with a candidate agent plus SoC arm at Day 29;
- Assuming the all-cause mortality rate through Day 29 is 15% for the concurrent placebo plus SoC arm of a candidate agent, a sample size of 350 patients per arm will provide 80% power to detect an absolute reduction of 6.75% (8.25% rate for the candidate agent plus SoC arm) in the mortality rate by Day 29. Assuming a mortality rate of 15% for the concurrent placebo plus SoC arm of a candidate agent and 19% for the candidate agent plus SoC arm (i.e., an adverse treatment effect of 4%) with a sample size of 350 per arm, the chance to observe a decrease in the mortality rate of at least 1% with a candidate agent plus SoC arm compared to its concurrent placebo plus SoC arm is approximately 4%.

The sample size calculation was performed using EAST 6.5.

CCI

PPD

Version Number: Amendment 1, v1.0
Version Date: 23Apr2021

CCI

For a sub-protocol where the primary analysis population is a subset of the randomized population, the sample size may be adjusted as applicable to power the designated primary analysis population as appropriate.

Each candidate agent may be evaluated for futility at up to two IAs (refer to Section 16.5).

7.2. MISSING DATA

Missing efficacy data will be handled as described in Sections 16.1.2, 16.2.2, and 16.3.2 of this SAP.

Missing safety data will not be imputed. Partially or completely missing AE and medication dates will be handled as described in Appendix 1.

7.3. STATISTICAL TESTS

Unless otherwise specified, all statistical tests will be conducted at the two-sided 0.05 significance level at the primary analysis. Confidence Intervals (CIs) will be two-sided with 95% coverage, unless otherwise specified.

7.4. MULTIPLE COMPARISONS/ MULTIPLICITY

No adjustment to control the family-wise type I error over the two IAs and the primary analysis of a candidate agent is needed as both IAs will be for futility only (refer to Section 16.5).

At the time of the primary analysis of each candidate agent, the primary efficacy endpoint will be tested at the 0.05 alpha level. Then, a hierarchical testing procedure will be used to test the three key secondary hypotheses (refer to Section 16.2.3.1). With this approach when a particular null hypothesis is rejected, the alpha allocated to that hypothesis can be reallocated to other hypothesis tests. The hierarchical testing procedure will be implemented in the following order:

1. Primary endpoint: Time to confirmed clinical recovery through Day 29, without re-hospitalization through Day 29 (refer to Sections 16.1.1 and 16.1.3);
2. Key Secondary endpoint: Incidence of oxygen-free recovery at Day 29 (refer to Sections 16.2.1.1 and 16.2.3.1);
3. Key secondary endpoint: Incidence of ≥ 2 -point improvement from baseline or fit for discharge on the ordinal scale at Day 29 (refer to Sections 16.2.1.2 and 16.2.3.1);

CCI

PPD

Version Number: Amendment 1, v1.0
Version Date: 23Apr2021

CCI

CCI [Redacted]

- 4. Key secondary endpoint: Incidence of all-cause mortality through Day 29 (refer to Sections 16.2.1.3 and 16.2.3.1).

In the hierarchical testing procedure, the formal testing can be performed for a step only when the statistical significance is declared for all the endpoints tested in the previous steps. If the testing sequence is stopped at a particular step, only nominal p-value will be provided for the remaining endpoints in the testing sequence.

Only nominal p-values will be provided for the non-key secondary endpoints and no statistical inference will be performed for the CCI [Redacted] and safety endpoints.

7.5. MULTICENTER STUDIES

This study will be conducted by multiple investigators at multiple centers. For each sub-protocol, data from all patients included in the candidate agent plus SoC arm will be pooled together in the analyses of the sub-protocol, regardless of the patient’s centers. Similarly, data from all patients included in the control arm of the candidate agent will be pooled together in the analyses of the sub-protocol, regardless of the patient’s centers.

Statistical analyses will be adjusted for the countries. Subgroup analyses by country might be performed for the primary and key secondary efficacy endpoints (refer to Sections 7.7, 16.1.5, and 16.2.5).

If data are too sparse for at least one country (i.e., less than 10% of FAS patients, regardless of the treatment arm), countries will be pooled into regions based on geographical area (e.g., North America, Latin America, Western Europe, Eastern Europe, and Rest of the World). In that case, statistical analyses will be adjusted for regions instead of countries.

For each sub-protocol, determination of the countries or regions to be included in the statistical models will be finalized in a blinded fashion before a sub-protocol database lock for an IA or Primary Analysis (refer to Sections 4.2 and 4.3) based on emerging data.

7.6. ADJUSTMENTS FOR COVARIATES AND FACTORS TO BE INCLUDED IN ANALYSES

The analyses will be adjusted for the following covariates and factors. For details of their inclusion in the models, refer to Sections 16.1.3, 16.2.3, and 16.3.3.

- Baseline value of the concerned endpoint, when applicable;

CCI [Redacted]	[Redacted]	Version Number:	Amendment 1, v1.0
PPD [Redacted]	[Redacted]	Version Date:	23Apr2021
CCI [Redacted]	[Redacted]	[Redacted]	[Redacted]
[Redacted]	[Redacted]	[Redacted]	[Redacted]
[Redacted]	[Redacted]	[Redacted]	[Redacted]

- Baseline clinical severity score of 2 randomization strata (yes or no), as captured on the IWRS;
- Remdesivir at baseline randomization strata (yes or no), as captured on the IWRS;
- Country (or region; refer to Section 7.5).

Sensitivity analyses replacing the randomization strata as captured in IWRS by the randomization strata as derived based on the data captured on the electronic case report form (eCRF) might be performed if at least 10% of the patients are mis-stratified at the time of randomization for a stratification variable (refer to Section 16.1.4) i.e.,

- Baseline clinical severity score of 2 (yes or no) as captured on the *Ordinal Scale for Clinical Severity* page of the eCRF;
- Remdesivir use at baseline (yes or no) based on data collected on the *Concomitant Medications* page of the eCRF (i.e., medications that were taken by a patient on the day the patient was randomized to a sub-protocol).

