### 2.2 Background

Coronaviruses are single-stranded RNA viruses capable of causing life-threatening disease in humans and animals. The novel coronavirus SARS-CoV-2, first identified during an outbreak of viral pneumonia cases of unknown cause in China, binds via the angiotensin-converting enzyme 2 receptor located on alveolar cells and intestinal epithelia. The virus is mutating, indicating that virulence and transmission will shift over time, and showing diversity in critical surface protein. Evidence suggests there are 2 groups of SARS-CoV-2; L-type and S-type. S-type is the less aggressive (30%); the L-type is now the most prevalent version (70%) and is more aggressive.

Most of the initial SARS-CoV-2 infections outside of China were travel associated (ie, from people who had traveled from the infected regions of China to other countries), although person-to-person transmission of SARS-CoV-2 in other countries was quickly established. On 11 March 2020, reports of 118,000 cases and 4,291 deaths in 114 countries prompted the World Health Organization to declare COVID-19 a pandemic. Less than a month later, worldwide cases had reached over 3.5 million, with over 240,000 deaths attributed to COVID-19. By the end of March 2021, over 126 million cases of COVID-19 and over 2.7 million deaths had been reported globally.

Central to elucidating the epidemiology of SARS-CoV-2 is surveillance of the clinical characteristics and outcomes of individuals diagnosed with COVID-19. Traditional epidemiologic risk factors such as geographic variation, advanced age, and comorbid conditions have emerged as clear risk factors for COVID-19. Sex-related differences in COVID-19 health outcomes have also been reported; despite equal numbers of COVID-19 cases between sexes, fatality rates are higher in men than in women.

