## 2.0 BACKGROUND/RATIONALE IN SUPPORT OF APREMILAST IN COVID-19

Since the outbreak of the severe acute respiratory syndrome coronavirus 2 (SARS-CoV-2) infection (causing COVID-19) in December 2019, this rapidly evolving pandemic has infected 23,964,800 people and has claimed 820,989 lives globally (John Hopkins COVID-19 data source, as of 26 August 2020). Compared to the typical, annual influenza epidemic, COVID-19 is associated with a mortality rate that is 10-fold higher, with a disproportionately higher rate of death among the elderly and individuals with underlying comorbidities (Wu and McGoogan, 2020). Although the vast majority of patients appear asymptomatic, or present with mild symptoms, experience from China has revealed that 14% of patients present with severe disease and 5% have a critical presentation associated with respiratory failure, shock, or multi-organ system dysfunction (Wu and McGoogan, 2020). The morbidity and mortality associated with this illness has been significant; in the United States, 19% of COVID-19 patients with known disposition have required hospitalization, with 6% of all patients requiring intensive care unit (ICU) admission (United States Centers for Disease Control [US CDC], 2020b). The clinical course in severe cases of COVID-19 infection is characterized by a hyperinflammatory immune response and often a rapid progression to acute respiratory distress syndrome (ARDS), resulting in a high ICU mortality rate, ranging from 39% to 72% (United States Centers for Disease Control [US CDC], 2020a). These high ICU mortality rates from China were also observed in Italy, where the ICU mortality was 26% with worse outcomes observed for older patients ( $\geq 64$  years of age, 36%) compared to younger patients ( $\leq 63$  years of age, 15%) (Grasselli et al, 2020).

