The Master Protocol outlines the overall design of the study, including the population, inclusion and exclusion criteria, randomization scheme, primary, secondary, and exploratory endpoints, study design, statistical methodology, and planned analyses that are common for all candidate agents to be tested. The Master Protocol is structured such that multiple candidate agents from different pharmaceutical companies can be evaluated simultaneously. The plan is to add candidate agents as they are identified and/or to remove therapies based on results of interim analyses (IAs; e.g., due to futility or if they are considered unsafe). The shared placebo control group for a candidate agent will include only patients randomized during the same period in which the candidate agent is opened for enrollment (refer to Section 4.5). Patients will be randomized equally to either the candidate agent plus SoC or placebo plus SoC in a double-blind fashion. Patients who are randomized to placebo plus SoC will be subsequently randomized equally to a matching placebo corresponding to an available candidate agent whose sub-protocol the patient qualified for (i.e., a 2-stage randomization). Each patient in the placebo plus SoC group will receive one type of placebo. Therefore, patients may be aware of which sub-protocol they were randomized to but not whether they will receive active agent or placebo investigational product. The comparator group of a candidate agent will include patients randomized to any matching placebo for a candidate agent available at the time of randomization for that agent (refer to Section 4.5).

Patients will be screened on Day -1 (the day before the first dose of study treatment [candidate agent plus SoC or

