10. DEMOGRAPHIC AND OTHER BASELINE CHARACTERISTICS

The following demographic and other baseline characteristics will be reported for this study:

[figure not shown]
- Age (years) – in integers, calculated relative to date of consent:
 - As a continuous variable;
 - As a categorical variable ($\geq 18 - \leq 49$, $\geq 50 - \leq 64$, $\geq 65 - \leq 84$, or ≥ 85);
- Sex (male or female);

CCI

PPD

Version Number: Amendment 1, v1.0
Version Date: 23Apr2021

CCI

- Childbearing potential for female patients only (yes or no) and reasons if not of childbearing potential;
- Race:
 - American Indian or Alaska Native, Asian, Black or African American, Native Hawaiian or Other Pacific Islanders, White, multiple, not reported, or unknown;
 - White, Black or African American, others, not reported, or unknown;
- Ethnicity (Hispanic or Latino, not Hispanic or Latino, not reported, or unknown);
- Country;
- Region (if applicable, refer to Section 7.5);
- Height (cm);
- Weight (kg);
- Body Mass Index (BMI) (kg/m²);

Demographic and other baseline characteristics will be summarized overall and by treatment arm based on the FAS. The control arm of a candidate agent (refer to Section 4.5) will be further broken down by sub-protocol. No statistical testing will be carried out for any demographic or other baseline characteristic.

Demographic and other baseline characteristics data will be listed.

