16.2.3.1. Binary Endpoints

For the incidence of patients with oxygen-free recovery at Day 29 (refer to Section 16.2.1.1), incidence of patients with ≥ 2 -point improvement from baseline or fit for discharge on the ordinal scale at Day 29 (refer to Section 16.2.1.2), incidence of all-cause mortality through Day 29 (refer to Section 16.2.1.3), incidence of patients with clinical recovery at Days 8, 15 and 29 (refer to Section 16.2.1.8), and incidence of patients with sustained clinical recovery as confirmed by Day 60 follow-up (refer to Section 16.2.1.9), the number and percentage of patients with and without the event will be provided by treatment arm. For the incidence of all-cause mortality, primary reason of death will also be summarized by treatment arm.

For each of these endpoints, a logistic regression will be performed to test the difference between a candidate agent plus SoC and placebo plus SoC treatment arms, including the baseline clinical severity of 2 on the 8-point ordinal

scale for clinical severity (yes or no) stratification variable, remdesivir use at baseline (yes or no) stratification variable, both as captured on the IWRS, country (region; refer to Section 7.5), and treatment arm as factors. The estimate of the relative risk (risk difference) between the two treatment arms, the corresponding two-sided 95% Wald CI, and the p-value obtained from the logistic regression model will be provided.

The odds ratio (of candidate agent plus SoC vs. placebo plus SoC) for having the event at the specified Day and its two-sided 95% CI will also be presented.

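### No readable efficacy model in the Master SAP adjusts for age, so the three key secondary logistic tests give up a modest amount of power

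*SAP*

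**What the plan says.** Master SAP 7.6 opens with "The analyses will be adjusted for the following covariates and factors" and gives four items: the endpoint's own baseline value where there is one, the two randomization strata (severity 2 yes/no, remdesivir yes/no), and country or region. The model sections follow that list. The logistic models in 16.2.3.1 carry the two strata plus "country (region; refer to Section 7.5), and treatment arm as factors". The proportional-odds models (16.2.3.2) and the Cox models for the primary endpoint (16.1.3), Day 29 mortality (16.2.5) and Day 60 mortality (16.4.5) use the same terms. The imputation models in 16.2.4 do too.

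Age is available. Section 10 reports it "in integers, calculated relative to date of consent". Apart from the baseline tables, its only use is as a subgroup variable in four bands (7.7).

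The documents treat age as prognostic. Master Protocol 2.2 says geographic variation, "advanced age, and comorbid conditions have emerged as clear risk factors for COVID-19". The apremilast sub-protocol (COV-01-004), section 2.0, cites an Italian ICU series with "worse outcomes observed for older patients": 36% mortality at 64 years or over, 15% at 63 or under, 26% overall.

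**The concern.** A baseline variable that predicts the outcome, is complete, and cannot be influenced by treatment is the standard candidate for adjustment. Leaving it out of a logistic model lowers the power of the treatment test. The severity term separates grade 2 from grades 3 to 5 only, so prognostic differences within grades 3 to 5 are not modelled, and age would carry some of them.

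A wish to confine the models to randomization factors does not explain the omission. Master Protocol 9.3.2 names only the two strata, and the SAP has already added country, which was not stratified on. Of the geography and age that Protocol 2.2 names together, only geography entered the models.

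At stake are the three key secondary tests, each planned at about 80% power. They are tested in sequence after the primary (7.4), so power lost at oxygen-free recovery, the first of them, also lowers the chance that the later two, including mortality, are formally tested.

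**Working it through.** **Inputs from the plan.** Allocation: "Patients will be randomized equally to either the candidate agent plus SoC or placebo plus SoC in a double-blind fashion" (SAP 3.1). Size: "350 patients are needed per arm in order to observe 490 confirmed clinical recovery events between the 2 treatment arms being compared" (SAP 7.1). Level: "all statistical tests will be conducted at the two-sided 0.05 significance level at the primary analysis" (SAP 7.3). Rates from SAP 7.1: mortality 15% vs 8.25%; oxygen-free recovery 65% vs 74.7%; 2-point improvement or fit for discharge 70% vs 79.2%.

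**Step 1: reproduce the stated power.** For two proportions with n = 350 per arm, power = Φ[(|p1 − p0| − 1.96·SE0)/SE1], with SE0 from the pooled and SE1 from the unpooled variance. For mortality SE0 = √(2 × 0.11625 × 0.88375/350) = 0.02423 and SE1 = √((0.15 × 0.85 + 0.0825 × 0.9175)/350) = 0.02410. So power = Φ[(0.0675 − 0.04749)/0.02410] = Φ(0.83) = 79.7%. The other two give 80.0% each. All match the plan's 80%.

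**Step 2: the only age gradient in the documents.** Odds ratio = (0.36/0.64)/(0.15/0.85) = 3.19. Share of older patients = (0.26 − 0.15)/(0.36 − 0.15) = 0.52. It comes from ICU patients and is unadjusted for severity, so using it here is an assumption.

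**Step 3: Wald power without age.** For mortality the log odds ratio is ln(0.0825/0.9175) − ln(0.15/0.85) = −0.674. Its SE is √(1/(350 × 0.15 × 0.85) + 1/(350 × 0.0825 × 0.9175)) = 0.245. Power = Φ(0.674/0.245 − 1.96) = 78.5%.

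**Step 4: Wald power with age.** The model is logit p = a + t·arm + ln(OR)·age. The values a and t are solved so that the arm-level rates stay at the plan's values, and SE(t) comes from the Fisher information.

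| Assumed age effect | Mortality | Oxygen-free recovery | 2-point or fit for discharge |
|---|---|---|---|
| Age not in model | 78.5% | 79.6% | 79.5% |
| Two groups, OR 3.19, 52% older | 79.6% | 82.1% | 81.8% |
| OR 1.25 per SD | 78.7% | 80.0% | 79.9% |
| OR 1.5 per SD | 79.2% | 80.8% | 80.6% |
| OR 2.0 per SD | 80.5% | 82.9% | 82.6% |
| OR 2.5 per SD | 81.9% | 84.9% | 84.5% |
| OR 3.0 per SD | 83.2% | 86.6% | 86.1% |

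For mortality, ORs of 1.25 to 3.0 per SD are worth having about 352 to 395 patients per arm instead of 350.

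**Step 5: simulation check for mortality.** In 4,000 trials per setting, both models also adjusted for a severity stratum (assumed 10% prevalence, OR 4). The gain was 1.2, 1.8, 3.7 and 4.8 points at ORs of 1.5, 2.0, 2.5 and 3.0 per SD. Type I error, with or without age, lay between 4.2% and 5.4%.

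**Step 6: where the gain sits.** At OR 2.0 per SD the mortality SE rises from 0.245 to 0.251 while the log odds ratio moves from −0.674 to −0.709, so the ratio goes from 2.75 to 2.82. On the risk-difference scale the variance falls by 4.9% (mortality) and 8.6% (oxygen-free recovery). With the ICU gradient the falls are 2.8% and 6.6%.

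**The case against.** The case for leaving the plan alone is that nothing in it is wrong. The SAP pre-specifies both strata and country, tabulates age by arm, and repeats the primary and key secondary analyses by age band. On the one gradient the documents offer, mortality gains about a point. That gradient describes ICU patients with 26% mortality, whereas this trial enrolls grades 2 to 5 and assumes 15%. The larger gains rest on odds ratios that the documents do not supply. The calculations also leave out country and remdesivir, so age's contribution given the full SAP model could differ. Most of the models listed carry no formal test: proportional-odds p-values are nominal (7.4), the Day 29 mortality Cox model is supplementary (16.2.5), and Day 60 mortality has no inference (16.4.3).

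All of that stands, and it sets the size of the point. It does not remove it. Tables and subgroups do not recover power in the main test, and the covariate is already in the database.

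A reader might infer that mortality loses most. The table shows the reverse: at an equal age odds ratio mortality gains least, because it is the rarest outcome. The ranking could change only if age predicted death clearly more strongly than non-recovery, and the documents give no age gradient for recovery. A reader might also expect a narrower interval for the odds ratio. Step 6 shows that its SE grows; the gain is in power, or in the precision of a standardised risk difference.

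**Conclusion.** The point holds as a modest, nearly free improvement to the three key secondary logistic tests. Assuming the cited ICU gradient, mortality power rises by about 1 point and oxygen-free recovery by about 2.5 points (79.6% to 82.1%), the latter only if the gradient carries over to recovery. Over assumed ORs of 1.25 to 3.0 per SD, mortality gains about 0.2 to 5 points.

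The documents do not support a reading that the planned comparison is invalid. Omitting age does not bias a randomized comparison, and type I error stays near 5%; a chance age imbalance is already covered by the test's error rate. Nor is the primary result affected: its test is a stratified log-rank test, and age in the accompanying Cox model would not change it.

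The reach is limited. The sub-protocol SAPs for COV-01-001 and COV-01-005 make no efficacy inference after early termination. COV-01-004 takes its efficacy analyses from the Master SAP unchanged, so the point bears on that agent and any later one. The exploratory models in 16.3 are redacted and cannot be checked.

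**What to change.** Before unblinding, add age at consent, as a continuous term, to the list in 7.6 and to the logistic models in 16.2.3.1. Add it to the matching imputation models in 16.2.4 so that imputation and analysis agree. Section 16.2.3.1 already plans a risk difference; report it as a standardised one from the fitted model, since that is the scale on which precision improves. For consistency, add age to the proportional-odds models (16.2.3.2) and the mortality Cox models (16.2.5, 16.4.5). Leave the primary log-rank test and its Cox hazard ratio as they are.

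The cost is small: one covariate, collected for every patient. The covariate text in Master Protocol 9.3.2 and 9.3.3 needs aligning, or the change recorded in SAP 3.3. The rule in 16.2.5 that drops a model factor from its own subgroup analysis should say what happens to continuous age within the age bands.
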